APPENDIX F. SCHEDULE OF ASSESSMENTS FOR PART D EXTENSION

Schedule of Assessments for the 90-day Extension in Subjects with Classic Galactosemia (Part D Extension)^a

PROCEDURE	Prescreening	Screening (Day -60 to -1) ^b	Day -1 ^c	Day 1	Day 2 ^d	Day 30 ^c	Day 60 ^c	Day 90 ^c	Day 91	EOE Visit ^e Day 118
Check-in			X					X		
Discharge					X				X	
Informed consent		X ^f	X ^f							
I/E criteria		X	X							
Medical history/updates	X (only CG diagnosis)	X	X							X
Demographic data		X ^g								
Physical examination ^g	X	X	X			X	X	X		X
Vital signs ^h		X	X	X	X	X	X	X		X
Electrocardiogram ⁱ		X	X	X		X	X	X		X
Clinical laboratory testing ^j	X ⁱ	X ^j	X ^j			X	X	X		X
GALT activity in red blood cells and GALT gene analysis	X ^q	X ^q								
Aldose Reductase activity		X ^q								
HIV and hepatitis B & C testing ^j	X	X								
Urine drug screen		X	X							
Pregnancy test (female subjects) ^k		X ^k	X ^k			X	X	X		X
Drug administration ^m						X				
Blood sample collection for PK analysis ⁿ				X		X	X	X	X	
Blood sample collection ^o for galactose, galactitol, galactose-1-p and other galactose metabolites		X		X		X	X	X	X	
Urine sample for galactitol ^p	X	X								
Impact-of-disease interview									X	
Adverse events									Throughout Extension	
Prior/Concomitant medications		X							Throughout Extension	

CG = Classic Galactosemia; CRU = clinical research unit; EOE = end-of-extension; EOS = end-of-study; I/E = inclusion/exclusion; MAD = multiple ascending dose; PK = pharmacokinetic; QD = once daily.

- a: All visits beyond Day 2 have visit windows of +/- 2 days. However, Day 1 must be the day of the first dose (in the extension); Day -1 must be the day before the first dose; Day 90 must be the day of the last dose; Days 88 and 89 must be the 2 days before day of the last dose; and Day 91 must be the day after the last dose.
- b: Screening visit for the Part D Extension is needed for subjects who have not previously participated in Part D. For subjects who previously participated in Part D, this Screening Visit is only needed if Day 1 of the extension period will be >60 days after the last visit (EOS or otherwise) in Part D.
- c: Check-in will occur around 11 am on Day -1. On Day 90, subjects will arrive at the CRU after an overnight fast of at least 10 hours (and before breaking the fast) and before taking study drug. In lieu of overnight stays in the CRU, subjects may stay at a local hotel; subjects will abide by all study guidelines including overnight fasting. The Day 30 and Day 60 visits can be either home health or in-clinic visits.
- d: Discharge from the in-clinic stay will occur after all procedures for that day are done and the subject has stayed in the clinic for at least 24 hours after the first dose.
- e: The EOE visit will be scheduled for 28 (± 2) days after the last dose of study drug. The EOE Visit will not be required if subjects transition to the separate Open-Label Extension Study, in which case the study completion will be considered the completion of the Treatment Period at Day 91.
- f: The informed consent form needs to be signed at the first visit for the extension which may be either the Screening visit or the Day -1 check-in (see footnote b).
- g: All physical examinations will include weight; however, height will be measured only at screening (or prescreening). Prescreening does not include a physical examination (only height and weight).
- h: Vital signs will be measured at Screening (if applicable), every check-in, every check-out, predose (within 60 min before the dose) and 4 hours (± 10 minutes) after the dose on Days 1, 30, 60, and 90, once daily on all other visits, and at the EOE visit.
- i: Electrocardiograms will be performed at Screening (if applicable), Day -1 check-in, predose (within 60 min before the dose) and 2 hours (± 10 minutes) after the dose on Days 1, 30, 60, and 90, and at the EOE visit.
- j: Samples for clinical safety laboratory tests (hematology, chemistry, coagulation, urinalysis, UACR and UPCR) will be collected under fasting conditions. At the Screening visit only (i.e., only applicable to subjects for whom this visit is required and does not need to be repeated at screening if already done at prescreening), HIV and hepatitis B & C testing will also be done. Hematology, chemistry, and coagulation at the Screening visit (i.e., only applicable to subjects for whom this visit is required) does not need to be repeated if already done at prescreening and prescreening was within 60 days before the first dose of Part D Extension study drug. Clinical safety laboratory tests (hematology, chemistry, coagulation, urinalysis, UACR and UPCR) do not need to be repeated at Day -1 if already done at prescreening or screening and the prescreening/screening visit was done within 60 days before the first dose of Part D Extension study drug.
- k: Serum pregnancy tests will be done at Screening (if applicable), Day -1 (also urine test if serum test cannot be processed immediately), and EOE visits; urine pregnancy tests will be done at all other time points. From Days 1 through 90, pregnancy tests must be done (and the result negative) on dosing days before study drug is administered. A pregnancy test must be performed on Day -1 even if already performed earlier during the screening period.
- m: On Days 1, 2, and 90, study drug will be administered at the clinic. On Days 30 and 60, study drug will be administered during the visit (home health or in-clinic). All other doses of study drug will be taken at home QD with water in the morning (preferably after an overnight fast of ≥ 10 hours with the fast broken ≥ 2 hours after the dose). Study drug administration should be at approximately the same time of day (preferably 8 am) throughout the extension. Drug accountability (including dispensing and/or collecting) will be assessed at all visits during the 90 days of dosing.
- n: On Day 1, a predose (within 60 minutes before the dose) blood sample for PK will be collected. On Days 30, 60, and 90, blood samples for PK will be collected predose (24 hours [± 15 minutes] after the dose taken the day before and within 60 minutes before the dose administered on that day) and at 2, 4, 8, and 12 hours (± 5 minutes for all time points) after the dose. An additional sample will be taken on Day 91 at 24 hour after the Day 90 dose.
- o: With the exception of the blood sample for biomarkers taken Screening (for those subjects requiring a screening visit), the time points and allowable windows for the blood samples for biomarkers will match those for the blood samples for PK.

p: Urine spot collection for galactitol analysis to check the study entry criterion based on urine galactitol (applicable only to subjects requiring a screening visit because it is assumed that urine galactitol for subjects not requiring the screening visit remain in the study eligible range and does not need to be repeated if done at prescreening)q: Required only for de novo subjects (i.e., subjects who did not previously participate in Part D SAD and MAD and does not need to be repeated at screening if already done at prescreening).

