In Parts D, E, and D Extension, the clinical site staff (except for the unblinded pharmacist) and the subjects will be blinded to study treatment. The Sponsor/CRO will not be blinded to study treatment because the relationship between exposure in Parts D, E, and D Extension (subjects with galactosemia) vs. exposure in healthy subjects will need to be evaluated on an ongoing basis to ensure that AT-007 blood levels remain within the limits achieved in Part B. This process will minimize the number of subjects with galactosemia potentially exposed to plasma concentrations of AT-007 not previously tested and shown to be safe in healthy subjects.

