7.2. Pharmacokinetic (PK) Assessments

Blood and/or urine samples for PK assessments will be collected at the visits as indicated in the Schedules of Assessments for Parts A, B, C, D, E, and D Extension ([Appendix A](#), [Appendix B](#), [Appendix C](#), [Appendix D](#), [Appendix E](#), and [Appendix F](#), respectively). Instructions for collecting and processing blood and urine samples for AT-007 and possible AT-007 metabolite analysis will be provided in a separate laboratory manual. Plasma samples will be analyzed for AT-007 using a validated method. PK samples will be stored for possible future analysis of AT-007 metabolites.

Also, for subjects in Part C, a Day 7 lumbar puncture will be done to collect CSF for AT-007 measurement ([Appendix C](#)) using a qualified assay.

The PK parameters in [Table 8](#) will be determined for the SAD parts of the study (i.e., Part A, the single dose period of Parts D and E).

Table 8: PK Parameters of AT-007 After a Single Dose in Healthy Subjects (Part A) and Subjects with Classic Galactosemia (SAD Period of Parts D and E)

PK Parameter	Definition
C_{max}	Maximum concentration, determined directly from individual concentration time data
T_{max}	Time of the maximum concentration
λ_z	The observed terminal rate constant; estimated by linear regression through at least 3 data points in the terminal phase of the log concentration-time profile
$T_{1/2}$	The observed terminal half-life, calculated as: $T_{1/2} = \frac{\ln(2)}{\lambda_z}$
AUC_{last}	Area under the concentration-time curve from time-zero to the time of the last quantifiable concentration; calculated using the linear trapezoidal rule
AUC_{inf}	Area under the concentration-time curve from time-zero extrapolated to infinity; calculated as: $AUC_{inf} = AUC_{last} + \frac{C_{last}}{\lambda_z}$
$AUC_{Extrap} (\%)$	The percentage of AUC_{inf} based on extrapolation
C_{last}	The last quantifiable concentration determined directly from individual concentration-time data
T_{last}	Time of the last quantifiable concentration
CL/F	Clearance after extravascular administration, calculated as: $CL/F = \text{Dose}/AUC_{inf}$
Vz/F	Volume of distribution in the terminal phase, calculated as: $Vz/F = (CL/F)/\lambda_z$

The PK parameters in [Table 9](#) will be determined for the multiple dosing parts of the study (i.e., Part B, Part C, MAD period in Parts D and E, and Part D Extension).

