Table 9: PK Parameters of AT-007 During Multiple Dosing in Healthy Subjects (Parts B and C) and Subjects with Galactosemia (MAD Period of Parts D and E and Part D Extension)

PK Parameter	Definition
C_{max}	Maximum concentration, determined directly from individual concentration time data (Day 1 and Day of Last Dose)
T_{max}	Time of the maximum concentration (Day 1 and Day of Last Dose)
λ_z	The observed terminal rate constant; estimated by linear regression through at least 3 data points in the terminal phase of the log concentration-time profile (Day of Last Dose only)
$T_{1/2}$	The observed terminal half-life, calculated as: $T_{1/2} = \frac{\ln(2)}{\lambda_z}$ (Day of Last Dose only)
AUC_{tau}	Area under the concentration-time curve during the 24-hour dosing interval; calculated using the linear trapezoidal rule (Day 1 and Day of Last Dose) Note: If quantifiable data are not observed through 24 h postdose, AUC_{tau} will be estimated using extrapolation (from the time of the last reported concentration to 24 h) and AUC_{last} will also be reported.
AUC_{last}	Area under the concentration-time curve from time-zero to the time of the last quantifiable concentration; calculated using the linear trapezoidal rule (Day of Last Dose; Day 1 if quantifiable data are not observed through 24 h postdose)
AUC_{inf}	Area under the concentration-time curve from time-zero extrapolated to infinity; calculated as: $AUC_{inf} = AUC_{last} + \frac{C_{last}}{\lambda_z}$ (Day of Last Dose only)
$AUC_{Extrap} (\%)$	The percentage of AUC_{inf} based on extrapolation (Day of Last Dose only)
C_{last}	The last quantifiable concentration determined directly from individual concentration-time data (Day 1 and Day of Last Dose)
T_{last}	Time of the last quantifiable concentration (Day 1 and Day of Last Dose)
CL/F	Clearance after extravascular administration, calculated as: CL/F = Dose/ AUC_{tau} (Day X), where Day X = Day of Last Dose and Dose is the actual dose administered (mg/kg x kg). (Day of Last Dose only) Note: CL/F/kg may also be reported
Vz/F	Volume of distribution in the terminal phase, calculated as: Vz/F = (CL/F)/ λ_z (Day of Last Dose only) Note: Vz/F/kg may also be reported

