- i: On Day 1, blood samples for PK will be collected predose (within 60 minutes before the dose) and at 0.5, 1, 1.5, 2, 4, 6, 8, and 12 hours (± 5 minutes for all time points) after the dose. On Day 2, blood samples for PK will be collected predose (i.e., at 24 hours ± 5 minutes after the Day 1 dose and before the Day 2 dose). On Day 7, blood samples for PK will be collected predose (within 60 minutes before the dose) and at 0.5, 1, 1.5, 2, 4, 6, 8, and 12 hours (± 5 minutes for all time points) after the dose. Also, blood samples for PK will be collected at 24, 36, and 48 hours (± 5 minutes for all time points) after the Day 7 dose; these collections will be taken on Day 8 and Day 9.

**APPENDIX C. SCHEDULE OF ASSESSMENTS FOR PART C (MAD IN
HEALTHY SUBJECTS)**

Schedule of Assessments for MAD in Healthy Subjects (Part C)

PROCEDURE	Screening (Days -28 to -1)	Day -1 ^a (Check-in)	Day 1	Day 2	Days 3, 4, & 5	Day 6	Day 7	Day 8	Day 9 ^a (Check-out)	EOS Visit ^b (Day 35±2)
Check-in		X ^a								
Discharge									X ^a	
Informed consent	X									
I/E criteria	X	X								
Medical history/updates	X	X								X
Demographic data	X									
Physical examination ^c	X	X				X			X	X
Vital signs ^d	X	X	X	X		X	X	X	X	X
Electrocardiogram ^e	X	X	X				X			X
Clinical laboratory testing (biochemistry, hematology, coagulation, urinalysis) ^f	X	X				X				X
HIV and hepatitis B & C testing	X									
Urine drug/cotinine screen	X	X								
Pregnancy test (female subjects) ^g	X	X				X				X
Drug administration ^h			X	X	X	X	X			
Blood sample collection for PK analysis ⁱ			X	X			X	X	X	
Lumbar puncture ^j							X			
Adverse events									Throughout Study	
Prior/Concomitant medications	X								Throughout Study	

CSF = cerebrospinal fluid; EOS = end-of-study; FSH = follicle-stimulating hormone; HIV = human immunodeficiency virus; I/E = inclusion/exclusion; MAD = multiple ascending dose; PK = pharmacokinetic; QD = once daily.

a: Check-in will occur around 11 am on Day -1 and Discharge will occur on Day 9 after the blood sample for PK is collected at 48 hours after the Day 7 dose and all Day 9 procedures are done.

b: The EOS visit will be scheduled for 28 (±2) days after the last dose of study drug.

- c: All physical examinations will include weight; however, height will be measured only at screening.

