In Part E, on Day 1 dose, blood samples for PK will be collected predose (within 60 minutes before the dose) and at 0.5, 1, 1.5, 2, 4, 6, 8, 12, 24, 36, and 48 hours (±5 minutes for all time points) after the dose. On Days 12 and 32, blood samples for PK will be collected predose (within 60 minutes before the dose) and at 0.5, 1, 1.5, 2, 4, 6, 8, and 12 hours (±5 minutes for all time points) after the dose. On Day 13, a blood sample for PK will be collected predose (i.e., at 24 hours ±5 minutes after the Day 12 dose). On Day 33, blood samples for PK will be collected at 24 and 36 hours (±5 minutes for both time points) after the Day 32 dose. On Day 34, a blood sample for PK will be collected at 48 hours (±5 minutes) after the Day 32 dose.

For Part E, Urine for galactitol measurement will be collected over the 24 hours immediately before and the 24 hours immediately after the dose on Day 1. Urine for galactitol measurement will be collected over the 24 hours immediately after the dose on Days 12 and 32. For each collection of urine for galactitol measurement, an aliquot of the total urine collected will be

analyzed for creatinine. Also, a spot collection for urine galactitol measurement will be taken at screening.

For Part D Extension, blood samples for PK will be collected on Day 1, a predose (within 60 minutes before the dose) blood sample for PK will be collected. On Days 30, 60, and 90, blood samples for PK will be collected predose (24 hours [± 15 minutes] after the dose taken the day before and within 60 minutes before the dose administered on that day) and at 2, 4, 8, and 12 hours (±5 minutes for all time points) after the dose.

For Part D Extension, Urine spot collection for galactitol analysis to check the study entry criterion based on urine galactitol (applicable only to subjects requiring a screening visit because it is assumed that urine galactitol for subjects not requiring the screening visit remain in the study eligible range).

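### Day 1 PK parameters and the accumulation ratio are planned for the Part D Extension but cannot be computed from its sampling, and its exposure comparison with Part B uses unlike time grids

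*Protocol*

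**What the plan says.** Protocol Section 7.2 applies one parameter table, Table 9, to every multiple-dosing part. Its parameters "will be determined for the multiple dosing parts of the study (i.e., Part B, Part C, MAD period in Parts D and E, and Part" (the list closes by naming the Extension). Table 9 defines Cmax as "Maximum concentration, determined directly from individual concentration time data (Day 1 and Day of Last Dose"), and gives the same two days for Tmax, AUCtau, Clast and Tlast. Rac is a Day X value over a Day 1 value, and the note under the table sets Day X to Day 90 for the Extension. SAP Table 6-2 repeats all of this.

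The Extension schedule in Appendix F, footnote n, reads: "On Day 1, a predose (within 60 minutes before the dose) blood sample for PK will be collected". Sections 6.8.1 and 6.8.2 list no PK draw after the first dose on Day 1 or on Day 2, and SAP Section 3.1.7 agrees. On Days 30, 60 and 90 there is a pre-dose sample, then "2, 4, 8, and 12 hours". The protocol adds: "An additional sample will be taken on Day 91 at 24 hour after the Day 90 dose". SAP 3.1.7 gives the same post-dose times ("and at 2, 4, 8, and 12 hours (±5 minutes for all time points) after the dose") but leaves out the Day 91 sample.

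Part B (Appendix B, footnote i) samples Days 1 and 7 pre-dose and at "0.5, 1, 1.5, 2, 4, 6, 8, and 12 hours", then at 24 h. Part D uses those times on Days 1, 12 and 32.

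Protocol Section 5.2 gives the reason for an unblinded sponsor in Parts D, E and D Extension: exposure is compared with healthy subjects on an ongoing basis "to ensure that AT-007 blood levels remain within the limits achieved in Part B".

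**The concern.** The parameter tables were carried over to the Extension without being adapted to its sparse schedule. Two things follow.

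First, the report is committed to Extension parameters that have no data behind them. SAP Table 14.2.2de is the planned Extension PK parameter summary. It would have to leave rows blank or fill them with a substitute chosen after the data are in. The SAP 6.1.2 exclusion rule, which sets the pre-dose concentration against 5% of Day 1 Cmax, has no denominator in the Extension either.

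Second, the Section 5.2 comparison sets an Extension profile read at few times against a Part B profile read at more. A difference in Cmax or AUCtau could then come from the grid and not from the drug. Multiple-dose PK in subjects with CG is a secondary objective, and the Extension is the only 90-day exposure in the study.

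**Working it through.** **1. Count the samples.** Sources: Protocol Appendices B, D and F.

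| | Part B | Part D | Extension |
|---|---|---|---|
| Post-dose samples to 24 h, Day 1 | 9 | 9 | 0 |
| Post-dose samples to 24 h, last dose | 9 | 9 | 5 |
| Of these, before 2 h | 3 | 3 | 0 |

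**2. Day 1 parameters.** Each is read from post-dose concentrations, and the Extension has none on Day 1. Rac(AUCtau) = AUCtau(Day 90) / AUCtau(Day 1), so its denominator does not exist. No passage exempts the Extension or lets a Part D Day 1 profile stand in, and de novo subjects have no Part D profile. This step needs no assumption.

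**3. Direction of any Cmax difference.** The Extension times {0, 2, 4, 8, 12, 24 h} are a strict subset of the Part B times {0, 0.5, 1, 1.5, 2, 4, 6, 8, 12, 24 h}. For the same profile, the maximum over the subset can equal or fall below the maximum over the full set, but cannot exceed it.

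**4. Possible size.** The documents give neither Tmax nor half-life, so both are assumed: half-life 3, 5, 8 and 12 h, and single-dose Tmax 0.5 to 3 h. The model has one compartment with first-order absorption, at steady state, dosed every 24 h:

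C(t) ∝ ka/(ka − ke) × [e^(−ke·t)/(1 − e^(−24ke)) − e^(−ka·t)/(1 − e^(−24ka))]

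Here ke = ln 2 / half-life, and ka solves Tmax = ln(ka/ke)/(ka − ke). AUCtau uses the linear trapezoidal rule, as in Table 9. The exact area in these units is 1/ke.

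Example with half-life 3 h and Tmax 1 h: ke = 0.231 and ka = 2.683. The highest value is 0.797 on the Part B grid (at 1 h) and 0.687 on the Extension grid (at 2 h). The ratio is 0.687/0.797 = 0.862.

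Ranges across the four half-lives:

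| Tmax | Cmax, Extension / Part B grid | AUCtau, Extension / Part B grid | AUCtau, Part B grid / exact | AUCtau, Extension grid / exact |
|---|---|---|---|---|
| 0.5 h | 0.731–0.921 | 0.847–0.958 | 1.005–1.023 | 0.865–0.963 |
| 1 h | 0.862–0.953 | 0.879–0.961 | 1.010–1.039 | 0.913–0.970 |
| 1.5 h | 0.967–0.983 | 0.921–0.968 | 1.011–1.044 | 0.962–0.979 |
| 2 h | 1.000 | 0.951–0.975 | 1.012–1.046 | 0.986–0.995 |
| 3 h | 1.000 | 0.973–0.985 | 1.012–1.057 | 0.996–1.028 |

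AUCtau on the Extension grid is thus 1.5% to 15% below the Part B-grid value. Part of that gap arises because the Part B grid itself reads about 0.5% to 6% high by the linear rule.

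**5. Can a later ratio replace Rac?** Even at the longest assumed half-life (12 h), three days of dosing reach 1 − 0.5^(72/12) = 0.984 of steady state. Day 30 and Day 90 are both at steady state, so their ratio should be near 1 whatever the accumulation. It tests for PK that changes with time. There is no 24 h sample after the Day 30 dose, so the area both days share is AUC0-12.

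**The case against.** The mismatch over Day 1 parameters cannot be argued away, but its reach can.

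- **The sparse grid may be well chosen.** The sponsor had PK from Parts A and B and Cohort D2 before the Extension, and timed lumbar punctures to Tmax from Part B. Day 30 and Day 60 can be home-health visits. If Tmax is 2 h or later, the grid costs nothing in Cmax relative to Part B. This stands for the capsule. It does not settle the liquid suspension, which Protocol Section 5.3 uses only in the Extension.
- **The safety consequence is not shown.** A reader might infer that the check against Part B is biased toward finding Extension exposure acceptable. The documents do not support that. Section 5.2 names no Cmax or AUC threshold. Cohort DE1 is given 20 mg/kg and Cohort B4 is planned at 40 mg/kg, twice that dose. The notes to the study schematic say that DE2's start and dose do not depend on DE1 results, and no stated dose decision rests on DE1 PK.
- **Accumulation in CG is available elsewhere.** Cohort D2 gives the same 20 mg/kg with the full grid on Days 1 and 32. A reader might infer that the secondary PK objective cannot be met, but it does not depend on an Extension Rac. The limits are that D2 plans only 4 active subjects, dosed with capsules for 27 days.
- **Matching grids does not recover a missed peak.** If the suspension peaks earlier than the capsule, comparing both at 2 h and later still misses it. This stands, and calls for a stated limitation.

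**Conclusion.** Two statements hold.

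The first rests on the documents alone. For every Extension subject (up to 21 on active drug in Protocol Table 7; up to 12 in SAP Table 3-7), the planned Day 1 Cmax, Tmax, AUCtau, Clast, Tlast and Rac cannot be produced, and the SAP 6.1.2 rule based on Day 1 Cmax cannot be applied.

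The second is conditional. The comparison with Part B uses unlike grids. The resulting shortfall in Cmax depends on an unstated Tmax, and runs from none (2 to 3 h) to 27% (0.5 h with a 3 h half-life) in the assumed model. Some difference in AUCtau appears in every modelled case, at 1.5% to 15%, but it is not all error in the Extension. This is a comparability problem to correct in the plan. It is not evidence that over-exposure would be missed.

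**What to change.** 1. In Protocol Table 9 and SAP Table 6-2, remove the Day 1 parameters and Rac for the Part D Extension, and mark the SAP 6.1.2 Day 1 Cmax rule as not applicable there. Take accumulation in CG at 20 mg/kg from Cohort D2, as Day 32 over Day 1 AUCtau. Report Extension Day 90/Day 30 ratios of pre-dose concentration and AUC0-12 as a check for time-dependent PK, not as accumulation.
2. For any comparison of Extension exposure with Part B or Part D, also derive Part B Day 7 and Part D Day 32 Cmax and AUCtau on the 0, 2, 4, 8, 12, 24 h grid, and show them next to the full-grid values.
3. Add the Day 91 sample (24 h after the last dose) to SAP 3.1.7, since AUCtau on Day 90 needs it.
4. State as a limitation that a peak before 2 h, including one from the liquid suspension, cannot be seen in the Extension.

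While the Rac row is open, note that both documents print Rac(Cmax) with Day 1 AUCtau as its denominator, which also needs correcting.

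The cost is wording in two tables and a little re-derivation from concentrations that the plan already collects. No new samples are needed. The downside is that the matched comparison ignores the early samples in Parts B and D, which is why the full-grid values stay beside it.
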